#### 6.5.9 Cycle 2, Day 29 (C2D29) and all subsequent Cycle Day 29 visits (i.e., C3D29, C4D29, etc.)

The subject will have the C2D1 Safety Procedures detailed below performed prior to initiating study treatment (nivolumab 3 mg/kg IV). Required assessments and nivolumab administration windows include  $\pm 3$  days of scheduled visit.

- Adverse event assessment
- Concomitant medication collection
- Complete physical exam, including neurological exam, and KPS assessment
- Vital signs: When scheduled at the same visit as other procedures, vital signs should be measured prior to clinical laboratory assessments or research blood sample collection.
  - Weight (can be taken within 3 days of ipilimumab administration)
  - Vital signs will be assessed and documented prior to the infusion and then approximately 30 minutes after the completion of the infusion:
    - Temperature, resting blood pressure, pulse and respiration rate.
- Serum chemistry: sodium, potassium, chloride, bicarbonate, calcium, magnesium, phosphorous, glucose, albumin, creatinine, blood urea nitrogen (BUN), uric acid, ALT, AST,

CONFIDENTIAL

This material is the property of the NYU School of Medicine. Do not disclose or use except as authorized in writing by the study sponsor

total bilirubin, direct and/or indirect bilirubin, alkaline phosphatase (ALP), lactate dehydrogenase (LDH), amylase, and lipase.

- Hematology: WBC count, 3-cell differential (ANC, monocyte count, lymphocyte count), hemoglobin, hematocrit, and platelet count
- T cell subsets (CD3, CD4, and CD8 counts) at C2D1, C4D1, C6D1, and C8D1 only.
- Urinalysis: glucose, blood, pH, specific gravity, ketones, and urine protein
- Thyroid stimulating hormone (TSH), free T4
- Pregnancy test (urine or serum  $\beta$ -HCG) for women of child-bearing potential

**Study Drug:** **Nivolumab only** will be administered in an outpatient setting as an IV infusion at the specified doses (for details see Administration of Study Drugs, Section 5.3). The doses of study drug must be adjusted each cycle for changes in body weight of  $\geq 10\%$ . The weight used for dosing can be taken within 3 days of scheduled study drug administration.

## 6.6 Efficacy Procedures

### 6.6.1 Contrast-Enhanced Brain MRI

Efficacy assessment consisting of a **contrast-enhanced brain MRI** will be performed **every 8 weeks on study**,  $\pm 7$  days. On-study imaging should follow calendar days (every 8 weeks) and should not be adjusted for delays in cycle starts. Clinicians may repeat response assessment more frequently as clinically indicated.

Tumor assessments for all subjects should continue as per protocol even if dosing is delayed.

**Research MRIs (sodium MRI):** All patients will have a research MRI (sodium MRI) at each efficacy assessment timepoint (i.e., at each contrast-enhanced MRI timepoint corresponding to every 8 weeks on study,  $\pm 7$  days). Research MRIs will be performed on MRI equipment housed at the same NYU facility where patients obtain clinical MRIs.

### 6.6.2 Efficacy Assessment

**Local reading (investigator assessment)** will be used to determine eligibility and for participant management. Response Assessments will be performed on every brain imaging assessment performed on protocol per standard **RANO criteria**. However, due to the known for patient management, non-traditional iRANO criteria may be used.

- Refer to Appendix 3 for details on iRANO criteria, guidelines for assessing radiologic findings, and treatment algorithm for the assessment of progressive imaging findings in patients with neuro-oncological malignancies undergoing immunotherapy.

**Evaluable for objective response.** Only those participants who have measurable disease present at baseline (obtained within 14 days of Cycle 1, Day 1) scan and have received at least one dose of therapy will be considered evaluable for response. These participants will have their response classified according to the definitions stated in Appendix 3. (Note: Participants who exhibit objective disease progression or die prior to the end of cycle 1 will also be considered evaluable.)

### 6.6.3 Continuation of therapy pending confirmation of radiographic disease progression

**If using iRANO criteria for patient management**, iRANO recommends confirmation of disease progression on **follow-up imaging 3 months after initial radiographic progression** if there is no new

CONFIDENTIAL

This material is the property of the NYU School of Medicine. Do not disclose or use except as authorized in writing by the study sponsor

or substantially worsened neurological deficits that are not due to comorbid events or concurrent medication, and **it is 6 months or less from starting immunotherapy** (see Appendix 3 for iRANO criteria details). A decision of whether a patient should continue immunotherapy pending confirmation of radiographic disease progression should be established based on perceived benefits and risks. Continuation of immunotherapy may be considered pending follow-up imaging as long as subjects are deriving apparent clinical benefit with minimal and acceptable toxic effects.

By contrast, investigators may consider interrupting immunotherapy for subjects who need a substantial increase in corticosteroids (i.e., >4 mg of dexamethasone or equivalent per day) for evolving symptoms associated with brain edema or who have more than mild treatment-related toxic effects such as at least grade 2 irAEs. These guidelines are included to limit the likelihood of progressive immunotherapy-induced inflammatory changes leading to substantial deficits in otherwise stable or symptom-free patients. In such subjects, an interruption of immunotherapy dosing might be considered pending follow-up imaging.

Furthermore, investigators may discontinue or interrupt immunotherapy at any time if this option seems to be in the best medical interest of the subjects. As a general guidance, resumption of immunotherapy might be taken into account when systemic dexamethasone is decreased to 4 mg/day or less and the contrast-enhancing tumor burden is classified as stable disease, partial response, or complete response on a follow-up scan, or when relevant treatment-related toxic effects have resolved to grade 1 or less or pre-treatment baseline.

## **6.7 End of Treatment Procedures**

Nivolumab and ipilimumab administration will continue for 2 years or until progression of disease, unacceptable adverse event(s), subject withdrawal of consent, death or another event that meets criteria for subject withdrawal or treatment discontinuation as per protocol guidelines.

End of treatment assessments below will be performed within 7 days after decision to end treatment. If the date to end treatment is determined later than 14 days from last study drug treatment, then it can be combined with the 30-day visit outlined in 6.8.2.

- Adverse event assessment
- Concomitant medication collection
- Complete physical exam, including neurological exam, and KPS assessment
- Vital signs: weight, temperature, resting blood pressure, pulse and respiration rate.
- Serum chemistry: sodium, potassium, chloride, bicarbonate, calcium, magnesium, phosphorous, glucose, albumin, creatinine, blood urea nitrogen (BUN), uric acid, ALT, AST, total bilirubin, direct and/or indirect bilirubin, alkaline phosphatase (ALP), lactate dehydrogenase (LDH), amylase and lipase.
- Hematology: WBC count, 3-cell differential (ANC, monocyte count, lymphocyte count), hemoglobin, hematocrit, and platelet count
- Urinalysis: glucose, blood, pH, specific gravity, ketones, and urine protein
- Thyroid stimulating hormone (TSH), free T4
- Pregnancy test (urine or serum β-HCG) for women of child-bearing potential

## **6.8 Post-Treatment Procedures**

In this study, survival is a key endpoint. In addition, there is potential risk for delayed immune-related toxicities with study drug. **Therefore, post study follow-up is of critical importance and is essential to preserving subject safety and the integrity of the study.**

CONFIDENTIAL

This material is the property of the NYU School of Medicine. Do not disclose or use except as authorized in writing by the study sponsor

Subjects who discontinue study drug must continue to be followed for collection of outcome and/or survival follow-up data as required below until death or the conclusion of the study.

#### **6.8.1 Adverse Event Follow-up Post-Treatment:**

All participants will be followed until resolution or stabilization of any serious or reportable adverse events occurring during treatment or starting within 30 days of last study drug. Assessments may continue for ongoing reportable adverse events. Participants removed from protocol therapy for unacceptable adverse events will be following until resolution or stabilization of the adverse event.

#### **6.8.2 30-day and 90-day post-drug visits:**

A site visit is to be performed at 30 days ( $\pm 7$  days) and 90 days ( $\pm 14$  days) after the last study drug is given, unless the subject is unable to travel due to deteriorating medical condition, due to the potential risk for delayed immune-related toxicities. The visit will include the safety procedures detailed below:

- Adverse event assessment.
- Concomitant medication collection
- Symptom-directed physical exam and KPS assessment.
- Vital signs: weight, temperature, resting blood pressure, pulse and respiration rate.
- Pregnancy test (urine or serum  $\beta$ -HCG) for women of child-bearing potential
- \*Serum chemistry: sodium, potassium, chloride, bicarbonate, calcium, magnesium, phosphorous, glucose, albumin, creatinine, blood urea nitrogen (BUN), uric acid, ALT, AST, total bilirubin, direct and/or indirect bilirubin, alkaline phosphatase (ALP), lactate dehydrogenase (LDH), amylase and lipase.
- \*Hematology: WBC count, 3-cell differential (ANC, monocyte count, lymphocyte count), hemoglobin, hematocrit, and platelet count.
- \*Thyroid stimulating hormone (TSH), free T4

\*For the 90-day post-drug visit, serum chemistry, hematology, TSH, and free T4 are required only if study-related toxicity persists.

#### **6.8.3 Extended Follow-up Post-Treatment:**

Following the 90-day post-drug visit, all subjects will be contacted every 3 months ( $\pm 14$  days) to assess for study-treatment related toxicities, initiation of any new anti-cancer treatments, and survival status. Contact may be performed by a site visit, telephone contact, e-mail, or mail. The date of death, initiation of any new anti-cancer treatments and date of last contact should be documented if this information is available. All subjects will be followed post-treatment until death, withdrawal of permission to record at least survival data, or subject is lost to follow-up.

If a subject withdraws permission to record at least survival data after coming off treatment, this must be documented along with the date the subject withdraws permission as per details in Section 6.12.

Subjects will be considered lost to follow up if no medical records are available to be reviewed and two phone calls each to the subject and then the subject's next-of-kin (if the subject does not respond) are not returned over two consecutive 3 month periods.

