## **Study Assessments:**

### *Efficacy*

Efficacy assessment consisting of a contrast-enhanced brain MRI will be performed every 8 weeks on study,  $\pm 7$  days, until disease progression is documented or treatment is discontinued (whichever occurs later). Response Assessments will be performed on every brain imaging assessment performed on protocol per RANO criteria.

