### 7.2.2 Main Study Cohort - Phase II trial design

A single-stage design will be utilized to estimate overall survival, with a hypothesized 1yr-OS of 60%= $H_1$  and 35%= $H_0$ . We will enroll 24 patients; this design has a two-sided Type I error of 0.05 and a power of 80%.

For endpoint analyses, one year will be defined as 48 weeks (8 cycles) and two years will be defined as 96 weeks (16 cycles). Patients will be evaluated for radiographic responses by conventional contrast enhanced MRI every 8 weeks. Radiographic response assessments will be determined using RANO criteria for GBM.

1yr-OS and radiographic response rates will be estimated with exact 95% confidence intervals; with 24 patients, a 95% CI will be no more than 0.4 units wide. OS will be determined from the time of treatment initiation until the time of death due to any cause, with OS being censored at last follow-up if the patient remained alive. Patients who were last known to be alive and progression-free will be censored at the latest disease assessment. The Kaplan–Meier curves will be used to summarize OS and to estimate the medians.

PFS is defined as the time between treatment initiation and first occurrence of disease progression or death, and will be censored at last follow-up if the patient remained alive without disease progression. PFS is defined as the time from the first dose of study treatment to the earlier of disease progression or death due to any cause. Patients who initiate alternate anticancer therapy in the absence of documented progression will be censored at the latest disease assessment prior to initiation of such therapy. Patients with no post-baseline disease assessments will be censored at the Cycle 1 Dose 1 date unless death occurred prior to the first planned assessment (in which case the death will be considered a PFS event). The Kaplan–Meier curves will be used to summarize PFS and to estimate the medians.

Overall response rate (ORR) is defined as the proportion of patients who achieve best overall response of complete or partial response at any time after initiation of study treatment (prior to initiation of alternate anticancer treatment). Duration of response is defined as the number of months from the time criteria are first met for either CR or PR, until the first date that PD is objectively documented. The duration of objective response will be summarized descriptively using the Kaplan-Meier method.

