26. Ipilimumab will be administered every 6 weeks ( $\pm$ 5 days of scheduled visit) in an outpatient setting as an IV infusion. The ipilimumab dose will depend on individual body weight. The dose of ipilimumab must be adjusted each dose for changes in body weight of  $\geq$ 10%. Dose adjustments for changes in body weight of <10% will be at the discretion of the investigator. Ipilimumab administration will continue for all subjects for 2 years (96 weeks) or until disease progression, intolerable toxicity, death, or the subject meets another withdrawal criterion per protocol.
27. Contrast-enhanced brain MRI: A contrast-enhanced MRI must be obtained within 21 days of the first dose of study treatment. For response assessment, a contrast-enhanced brain MRI will be performed 8 weeks after study drug initiation, and then every 8 weeks thereafter. MRIs can be performed within 7 days ( $\pm$ 7 days) of scheduled assessment. On-study imaging should follow calendar days (every 8 weeks) and should not be adjusted for delays in cycle starts. Local reading (investigator assessment) will be used to determine eligibility and for participant management. Response Assessments will be performed on every brain imaging assessment performed on protocol per RANO criteria, although non-traditional iRANO criteria may be used for patient management (see **Appendix 3**).
28. Research Blood Samples: For all patients, whole blood will be drawn at two timepoints: At pre-dose C1D1 (-3 days) and at C2D1( $\pm$  3 days). Four purple top EDTA tubes (40 mL) will be drawn, one EDTA tube will be sent to the CBRD and three EDTA tubes will be sent immediately to the IMC.
29. Research (sodium) MRI: All subjects must have a research MRI performed prior to C1D1 (within 21 days of study drug initiation) and at every response assessment timepoint on study treatment (i.e., every 8 weeks after study drug initiation, and then every 8 weeks thereafter). Research MRIs can be performed within 7 days ( $\pm$ 7 days) of scheduled assessment. Research MRIs must be performed at NYUSoM.
30. Optional tumor biopsy: If subjects provided consent for optional on-study or post-study drug tumor biopsy collection, a tumor specimen will be collected for research purposes. For details see the study procedures.

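### The synopsis rule for MRI after treatment stops is not carried into the body or the schedules, and 7.2.2 gives two censoring points for progression-free patients

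*Combined protocol and SAP*

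**What the plan says.** **Imaging.** The synopsis (Study Assessments, Efficacy) schedules contrast-enhanced MRI every 8 weeks "until disease progression is documented or treatment is discontinued (whichever occurs later". A patient who stops for toxicity therefore keeps being scanned until progression. Section 6.6.1 gives the interval but no end point: "On-study imaging should follow calendar days (every 8 weeks) and should not be adjusted for delays in cycle starts". Footnote 27 of both schedules counts 8-weekly MRI from drug initiation, also without an end point.

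**After treatment.** Section 6.8 says that subjects who discontinue "must continue to be followed for collection of outcome and/or survival follow-up data as required below". What follows is safety visits at 30 and 90 days ("The visit will include the safety procedures detailed below") and then 3-monthly contact "to assess for study-treatment related toxicities, initiation of any new anti-cancer treatments, and survival status", which may be by telephone, e-mail or mail. Sections 6.7 and 6.8 list no MRI. In Appendices 1 and 2 the MRI row is blank under End of Rx, 30-day, 90-day and survival follow-up.

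**Analysis.** Section 7.2.2 says PFS "will be censored at last follow-up if the patient remained alive without disease progression". The OS paragraph of the same section says that patients last known to be alive and progression-free are censored at their most recent disease assessment. Duration of response runs to objectively documented progression, and no censoring rule is given.

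**The concern.** Stopping before progression is built into the design, through dose-limiting toxicities, the drug discontinuation lists and the edema rules. Patients who finish the 96 weeks of treatment without progression are in the same position. A site working from 6.8 and the schedule grids could stop scanning these patients when treatment ends, although the synopsis says otherwise.

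Three secondary endpoints in both cohorts depend on what happens next.

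- **PFS:** a patient who is no longer scanned may be counted as progression-free until death or the last contact.
- **Duration of response:** it ends only at documented progression, so it has no defined end once scanning stops.
- **Response rate:** a response first seen on the last on-treatment scan has no confirming scan in the post-treatment columns. The response appendix (15.4) counts an unconfirmed response as stable disease, which pulls the response rate down.

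**Working it through.** **1. Passages side by side**

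| Place | Imaging or progression after treatment stops |
|---|---|
| Synopsis, Efficacy | MRI every 8 weeks until the later of progression or discontinuation |
| 6.6.1 | Every 8 weeks while on study; no end point |
| Footnote 27, both schedules | Every 8 weeks from drug initiation; no end point |
| 6.2.4 | Best effort to document progression after stopping, in the paragraph on symptomatic deterioration |
| 6.7, 6.8.2 | No MRI; KPS assessed |
| 6.8.3 | Toxicity, new therapy and survival; no progression status |
| Schedule grids, post-treatment columns | MRI row blank |

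Nothing in the body contradicts the synopsis outright, but no post-treatment section or column carries its rule.

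**2. Size: an illustration**

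The plan gives no figure to reproduce. Inputs:

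- Time to progression: exponential, median 6 months (the standard-therapy PFS in 3.1.3). Rate λ = ln 2 / 6 = 0.1155 per month.
- Progression to death: exponential, median 6 months (assumed).
- A toxicity stop assigned to a fraction f = 20%, 30% or 40% of patients, uniform over months 1 to 5 (assumed), and effective only if it precedes progression.
- Scan interval: 56 / 30.4375 = 1.84 months.

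The share stopping before progression is f × (e^(−λ) − e^(−5λ)) / (4λ) = f × (0.891 − 0.561) / 0.462 = 0.71 f. That is about 14%, 21% and 28%, or 0.14 × 24 = 3.4 to 0.28 × 24 = 6.7 patients: about 3 to 7 of 24.

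In rows A to D these patients are held event-free until death. All others have their event at progression (A) or at the next 8-week scan (B to D).

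| | No stops | f = 20% | f = 30% | f = 40% |
|---|---|---|---|---|
| A. Median PFS (months), progression dated exactly | 6.0 | 6.7 | 7.2 | 7.7 |
| B. Median on the scan grid, stop before progression | 7.4 | 7.4 | 7.4 | 8.4 |
| C. Median on the scan grid, stop before the detecting scan | 7.4 | 7.4 | 7.9 | 9.2 |
| D. 12-month PFS under C | 27.8% | 32.9% | 35.6% | 38.0% |
| E. Median as A, but censored at the last on-treatment scan, later deaths ignored | 6.0 | 5.8 | 5.7 | 5.5 |

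Medians that fall between scan dates vary by about 0.1 month from run to run. With exponential rather than uniform stop times, the grid median stays at about 7.4 with 11% to 33% stopping and reaches 9.2 with 43%.

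**3. Reading the table**

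On the grid the median moves in steps of up to 1.84 months, so an unchanged median does not show an absence of bias: row D rises even at f = 20%, where rows B and C stay flat. Row E shows that the direction depends on the censoring rule. Row E also ignores later deaths, whereas 7.2.2 counts death as a PFS event. A single censoring sentence therefore settles only the patients who stay alive. For those who die off treatment, only a documented progression date corrects the PFS time.

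**The case against.** The strongest reply is that the plan already holds most of what is needed. The synopsis rule is protocol text. Footnote 27 has no stop at discontinuation and is compatible with it. On study need not mean on treatment: 6.10.1 keeps subjects who ask to stop the drug in the study, and 6.2.4 speaks separately of a treatment phase. Clinical deterioration counts as progression under 15.4, and KPS is assessed at end of treatment and at 30 and 90 days. Section 6.6.1 lets clinicians repeat response assessments as indicated, so a late response can still be confirmed. Section 7.2.2 already contains a sentence using the most recent disease assessment, and patients who start new therapy are censored at their latest assessment before it.

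All of this stands, and it limits the point. It rules out the reading that the schedules contain no imaging, or that PFS is unmeasured in these patients. The sodium-MRI footnote, "at every response assessment timepoint on study treatment", does not help that reading either, because it governs the research scan and not the efficacy MRI.

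It does not close the gap. After day 90 no scheduled contact asks about progression. The 6.2.4 sentence is best effort and sits with symptomatic deterioration. The helpful censoring sentence is in the OS paragraph, while the PFS paragraph says something different.

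**Conclusion.** The point holds as an inconsistency between the synopsis and the body, joined to two conflicting censoring sentences. Off-treatment progression is incompletely documented, and duration of response has no censoring rule when scanning stops.

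A reader might infer that PFS will be biased upward by a known amount. The documents do not support that. Upward bias follows if the last-follow-up rule is applied with contact-only follow-up. Its size depends on the share stopping before progression, which has no source in the documents, and on the scan grid. The illustration also leaves out clinical progression and censoring at new therapy. It gives 0.7 to 1.7 months on the median with exact dating (6.7 − 6.0 and 7.7 − 6.0) and anything from no change to 1.8 months (9.2 − 7.4) on the grid.

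A reader might also infer that the primary endpoint is at risk. One-year OS does not depend on imaging. The only contact is the misplaced sentence: taken literally, it would censor OS at a scan date in patients known to be alive later. The affected endpoints are secondary, single-arm and descriptive, but missed scans cannot be recovered afterwards, so the text should be corrected.

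**What to change.** - **6.6.1, 6.7, 6.8 and both schedules:** reconcile with the synopsis, so that one rule states what imaging and RANO assessment applies to patients off treatment without progression, and mark it in the post-treatment columns.
- **6.8.3:** add progression status, date and basis (scan or clinical) to the 3-monthly contact.
- **7.2.2, censoring:** state one rule that censors PFS and duration of response at the last adequate disease assessment. Say how a death after missed assessments is handled, since PFS counts death as an event.
- **7.2.2, OS paragraph:** move the disease-assessment sentence to PFS, so that OS is censored only at the date last known alive.

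The cost is wording in these sections and two tables, plus the work of collecting off-treatment scan data. No scan is added beyond those the synopsis requires, and 1.3.4 describes imaging about every 2 months as equivalent to standard care.
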